
Investigation project
		

Pontificia Universidad Javeriana. As a result, it is expected to select 66 individuals, 50% men and 50% women, who meet the inclusion criteria. Individuals will be stratified by sex and will be randomized in equal numbers to each of the three treatment groups, such that each treatment group will have 33 people in which the sexes will be equally distributed.

The sample size was determined taking into account the literature in which the same biomarkers have been evaluated (Brenna, Plourde, Stark, Jones, & Lin, 2018; Gonzales & Gonzales, 2014; Nayebifar, Ghasemi, & Karimipour, 2020; Qureshi, Sami, Salser, & Khan, 2001, 2002). It is important to highlight that to date there are no studies that contemplate the two oils carried in a fermented drink; even though there are studies with hybrid palm oil, alone and in other foods, there are none with Sacha Inchi oil, for the postulated response variables. Upon encountering this panorama, this study will provide a parameter to determine the sample size in subsequent studies. Finally, the postulate of the Food and Drug Administration (FDA) was taken into account, which states that the total number of subjects and patients included in Phase 1 studies varies with the drug, but is generally in the range of 20 to 80 subjects (FDA, 2019), so it is considered that it can also be applied as a criterion for foods since the guidelines for drug testing are rigorous.

Following these criteria, it was determined to take 54 subjects in total with an oversample of 20% (66 individuals in total) to compensate for possible dropouts during the follow-up stage. Compliance with the proposed number of participants and the collection of their blood samples will be subject to the evolution of the Covid-19 pandemic and government preventive isolation guidelines.

Target population

Inclusion criteria: adult men <50 years old and women <40 years old, healthy, with TC levels $\geq 200\text{mg/dl}$, with regular consumption of fermented milk beverages at least three times/week, with a maximum level of moderate physical activity and who sign the informed consent.

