Exclusion criteria: TG $>700\text{mg/dl}$, hyperlipidemia undergoing pharmacological treatment, drug or alcohol addiction, smokers, history of allergy to red palm olein and/or milk and its derivatives, consumption of nutritional supplements, being pregnant or breastfeeding, having menopause, presence of chronic disease (HTN, Diabetes Mellitus, among others) and a BMI >29.9

The sample will be selected using a convenience criterion through a call at the Pontificia Universidad Javeriana. Individuals will be stratified by sex and randomized using the method called “unrestricted randomization” to the three groups. The size was determined considering the literature in which the same biomarkers have been evaluated (Brenna, Plourde, Stark, Jones, & Lin, 2018; Gonzales & Gonzales, 2014; Nayebifar, Ghasemi, & Karimipour, 2020; Qureshi, Sami, Salser, & Khan, 2001, 2002). The FDA postulate was considered, which states that the total number of subjects included in Phase 1 studies varies with the drug but is generally in the range of 20 to 80 subjects (FDA, 2019). Following these criteria, it was determined to take 54 subjects in total with an oversample of 20% (66 individuals in total), each group with 21 subjects to compensate for possible dropouts and guarantee 18 per group. Each participant must sign an informed consent.

 
Pontificia Universidad JAVERIANA Colombia
	Research registration PUJ	Version: 1
	Investigation project	

Development

The differential nutritional characteristics of the fermented milk drinks to be used in the study are presented below. It is important to clarify that all drinks will comply with current regulations for fermented drinks. (Ministerio de salud, 1986).

Table 1. Lipids and vitamin E in 200g of yogurts.

Characteristics (200g/yogurt)	Control yogurt	SIO yogurt	HPO yogurt
Total, lipids (%)	3	3	3
SFA (%)	2	7	35
MUFA (%)	0.8	10	56
PUFA (%)	0.1	85	12
Vitamin E (mg/100g)	0.06	6.09	2.88

SFA: saturated fatty acids, MUFA: monounsaturated fatty acids, PUFA: polyunsaturated fatty acids,

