The analyzes of TC, c-HDL, LDL and triglycerides will be determined by the enzymatic colorimetric method; Apo A and Apo B by immunoturbidimetry and vitamin E by HPLC, in the clinical laboratory of the San Ignacio University Hospital. Each phase of the study includes supervision and support actions for participants to promote and generate adherence (Ministerio de Salud y Protección Social & Colciencias, 2014)). The intervention phase follows the recommendations of the European Food Safety Authority for claims related to cardiovascular health (Turck et al., 2018). Diagram 1 shows the study design, which consists of three phases.

Phase I

1. Screening in the anthropometry laboratory of the Faculty of Sciences of the PUJ, which consists of the following activities:
 - a. Characterization of individuals to know their sociodemographic data (age, sex, educational level, economic status).
 - b. Application of a morbidity survey, to know their diseases, clinical history, biochemical parameters, cardiovascular risk (using the Framingham risk scale)
 - c. Evaluation of body composition by dual X-ray absorptiometry - DEXA (lean mass, fat mass, bone mass, mineral density), estimation of BMI and measurement of abdominal circumference.
 - d. Exploration of eating habits (consumption frequency questionnaire and 24-hour recall).
2. Training
 - a. Record consumer diaries three days a week (two weekdays and one weekend day) and will be informed that they will receive a weekly, unannounced phone call for a 24-hour reminder and survey. about the level of physical activity.
 - b. Preparation for taking blood samples in accordance with the protocol of the San Ignacio University Hospital.

 Pontificia Universidad JAVERIANA Colombia	Research registration PUJ Investigation project	Version: 1
--	--	-------------------

[figure not shown]

Figure 1. Study design.

Phase II

The subjects will continue with their usual diet with a modification in their pattern of consumption of milk and dairy products, since fermented milk drinks will be supplied at a rate of 250g/day for one month. These will be prepared following good food handling practices (Ministerio de Salud y Protección Social, 2013), in the pilot research plant in milk and dairy products processes, of the National University of Colombia, Bogotá headquarters. All raw materials are safe for human consumption (GRAS). Through unrestricted random sampling, subjects will be assigned into three branches:

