1. Control: corresponds to the subjects who will be given a fermented milk drink
2. Treatment 1 corresponds to the subjects who will be supplied with the fermented milk drink with total replacement of milk fat matter with SIO.
3. Treatment 2 corresponds to the subjects who will be supplied with the fermented milk drink with total replacement of milk fat matter with HPO.

 
Pontificia Universidad JAVERIANA Colombia
	Research registration PUJ	Version: 1
	Investigation project	

Phase III

In this phase, the results will be shared with the study participants and a final assessment.

Statistical analysis

A socio-economic-demographic characterization of the population will be carried out, by means and standard deviation and ranges. A database will be created in Excel and the intake will be analyzed using the Menus Plus 2018 software. To analyze data from blood samples, a repeated measures analysis of variance will be applied. Kolmogorov and Cramér-von Mises tests will be used to evaluate the Gaussian nature of the variables. Tukey-adjusted p values will be applied to examine differences between treatments. STATGRAPHICS CenturionXVIII software will be used.

POSSIBLE RESEARCH RESULTS

With this research, the characterization of the nutritional status, health status and quality of the diet of the target population will be obtained. Furthermore, after the intervention with fortified yogurts, it is expected to observe an improvement in the blood lipid profile parameters, Apo A, Apo B and vitamin E, of the participants compared to the initial values, which would minimize the risk of associated CVD associated to lipoproteins.

Expected products

Category	Product	Amount	Description
Other outreach products	Documentary Production	1	Submission of at least 1 scientific article in an indexed journal.
Presentation at scientific event	Presentation of paper or poster at international event	1	Participation in a conference related to the topic of clinical nutrition or food science and technology.
Project formulation and submission	Formulation and submission of other projects	1	Another project related to the characterization of the mechanism of the bioactive compound.

PARTICIPATING INSTITUTIONS

Participating entity/institution name	Temporal	Main financier	Other financier	Executor	Co-Executor	Assesment entity
UNIVERSIDAD NACIONAL DE COLOMBIA - BOGOTÁ	No	No	Yes	No	Yes	No
PONTIFICIA UNIVERSIDAD JAVERIANA (PUJ)	No	Yes	No	Yes	No	No

TEAM OF PONTIFICIA UNIVERSIDAD JAVERIANA

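### Equal arms, an equal sex split and 18 per group are promised, but the named 'unrestricted' randomisation secures none of them, and the stated arm sizes do not add up to 66

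*Combined protocol and SAP*

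**What the plan says.** All of this is in the combined protocol and SAP.

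- **Type of study, total:** "it is expected to select 66 individuals, 50% men and 50% women, who meet the inclusion criteria".
- **Type of study, allocation:** "Individuals will be stratified by sex and will be randomized in equal numbers to each of the three treatment groups". The sentence goes on to say that "each treatment group will have 33 people in which the sexes will be equally distributed".
- **Target population, method:** "Individuals will be stratified by sex and randomized using the method called “unrestricted randomization” to the three groups".
- **Target population, arm size:** after repeating 54 subjects plus a 20% oversample, 66 in all, it gives "each group with 21 subjects to compensate for possible dropouts and guarantee 18 per group".
- **Development, Phase II:** "Through unrestricted random sampling, subjects will be assigned into three branches".
- **Statistical analysis:** "To analyze data from blood samples, a repeated measures analysis of variance will be applied". No sex term is named.

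The available text describes no block, list or other mechanism that would produce the promised balance.

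**The concern.** There are two separate faults.

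The first is that the promise and the method do not match. The sponsor chose to stratify by sex and to have equal arms. Unrestricted randomisation is normally the name for simple randomisation, in which each person is allocated independently of everyone before. Done separately in men and in women it is still simple randomisation, so the stratification has no effect on the allocation. The arm sizes and the sex split within each arm are left to chance.

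The second is that three figures (66 in total, 33 per arm, 21 per arm) cannot all be right, and no two of them agree.

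With arms of about 20 people, chance imbalance can be noticeable. The analysis names no sex factor that would adjust for it. The figure of 18 per group is the only post-dropout number per arm in the plan, and nothing in the design secures it. Whoever runs the allocation cannot tell from the text which procedure or which arm size to use.

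**Working it through.** **Inputs from the documents.** Total 66, half men and half women, so 33 of each; three arms in equal numbers (Type of study). Base size 54 with a 20% oversample (Type of study, Target population). Arm size 33 (Type of study) or 21 (Target population). 18 per group after dropout (Target population).

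**Assumptions.** Unrestricted means independent draws with probability 1/3. Dropouts are independent. The plan states an oversample but no expected dropout rate, so a range is shown.

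**Step 1: the total of 66.** 54 × 1.2 = 64.8, and 54 / 0.8 = 67.5. The stated 66 lies between them and is the first multiple of 6 (three arms × two sexes) above 64.8. The total therefore fits the plan's own rule, and the error lies in the arm sizes.

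**Step 2: arm sizes.**

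| Per arm | × 3 | Equals 66? | Half of the arm |
|---|---|---|---|
| 33 | 99 | no | 16.5 |
| 21 | 63 | no | 10.5 |
| 22 (not stated) | 66 | yes | 11 |

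**Step 3: balance under simple randomisation of 66.**

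- Standard deviation of one arm's size: √(66 × 1/3 × 2/3) = 3.8.
- P(22/22/22) = 66! / (22!³ × 3⁶⁶) = 0.0124.
- P(11/11/11 within one sex) = 33! / (11!³ × 3³³) = 0.0246. For both sexes: 0.0246² = 0.0006.
- Enumerating every split of 66 into three arms: the mean gap between largest and smallest arm is 7.9 people, and P(some arm below 18 before any dropout) = 0.350.
- Enumerating every split of 33 men and 33 women: P(some arm outside 40–60% male) = 0.478, and P(male share differs by more than 20 percentage points between two arms) = 0.396.
- Precision: E(1/n₁ + 1/n₂) / (2/22) = 1.033, an average rise of 3.3% in the variance of a pairwise contrast.

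**Step 4: the guarantee of 18.** For arms fixed at n with dropout d, P(some arm ends below 18) = 1 − [P(Bin(n, 1 − d) ≥ 18)]³. For simple allocation, the probability that all three arms keep 18 is averaged over the multinomial arm sizes before it is subtracted from 1. The 18.2% row is the loss that takes 66 to 54 (12/66).

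| Assumed dropout | Simple, 66 in total | 22 per arm fixed | 21 per arm fixed |
|---|---|---|---|
| 0% | 35% | 0% | 0% |
| 5% | 53% | 1% | 6% |
| 10% | 72% | 18% | 39% |
| 15% | 88% | 54% | 77% |
| 18.2% | 94% | 75% | 91% |
| 20% | 96% | 84% | 95% |

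Fixed arms help clearly when dropout is low and little when it is near 20%. An arm of 22 can lose 4 people and still keep 18; an arm of 21 can lose 3.

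**The case against.** The strongest reply is that simple randomisation may not be what was meant. The Phase II wording speaks of sampling, and drawing groups of fixed size from a complete list is an ordinary meaning of random sampling. The Type of study section does ask for equal numbers by sex, which amounts to a quota, and the order of events (selection, screening, then assignment) is compatible with a closed list. On that reading the probabilities in step 3 and the first column of step 4 do not apply. This stands as a condition on those figures. It does not rescue the text: no such draw is described, nothing says that everyone is enrolled before allocation, unrestricted would be the wrong word for it, and the conflict between 33, 21 and 66 remains.

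Secondly, if the treatment effect is read from the treatment-by-time term, a stable difference in lipid level between men and women cancels within person. Sex imbalance then matters only if sex also affects the change. This is fair. The Statistical analysis section does not say which contrast is used, and the documents give no sex effect on change, so the imbalance figures describe the arms and not a distortion of any result.

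Thirdly, missing 18 per group is largely a matter of dropout. At the 18.2% loss implied by 66 and 54, even fixed arms of 22 leave some arm short 75% of the time. That is correct, and it is why the wording of the guarantee has to change as well as the method. The 54 itself rests on literature and a phase 1 range, with no power calculation, so falling below 18 has no stated consequence for power.

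The study-design figure was not available. Even if it shows arm sizes, the sentences in the text would still disagree.

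**Conclusion.** The concern holds. The arm-size conflict (99 and 63 against 66, with both arm sizes odd) is present on any reading. The mismatch between the promised balance and the named method holds for the text as written.

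Its size depends on what was meant. If simple randomisation was meant, exactly equal arms are very unlikely (1.2%), about one allocation in three starts with an arm below 18, and about two in five have male shares more than 20 points apart. No bias follows, and the average cost in precision is about 3%. If a fixed-quota draw was meant, the fault reduces to an undescribed procedure, a misleading term and wrong arm sizes.

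This should be corrected before allocation starts. It does not threaten the validity of the comparison.

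**What to change.** 1. **Method.** In both Target population and Phase II, replace the unrestricted wording with restricted randomisation within sex. One workable form is a concealed, computer-generated list for men and another for women, each with five blocks of 3 and three blocks of 6 in random order (5 × 3 + 3 × 6 = 33). This gives 11 per arm per sex if 33 of each enrol, and arms at most 2 apart within a sex if enrolment stops early. Other block layouts would serve. If everyone is enrolled before allocation, a random draw with fixed quotas within sex also works; if that was the intention, say so and state the quotas.
2. **Arm size.** Replace 33 and 21 with 66 / 3 = 22 (11 men and 11 women). The overall half-and-half sex split depends on recruitment, so state that enrolment is capped at 33 of each sex.
3. **Analysis.** Include sex as a factor in the repeated-measures model, to match the stratified allocation, and name the contrast that carries the treatment comparison.
4. **The 18.** Call it a target and state the dropout rate on which it rests. If 18 must be reached with high probability at a loss near 20%, 22 per arm is too few.

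The cost is a few sentences and a list generated in advance. Blocking makes allocation slightly more predictable; mixed block sizes and concealment limit this.

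### The plan allows for about 14% to 18% loss but names only a repeated-measures ANOVA, with no analysis set and no adjustment for baseline or sex

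*Combined protocol and SAP*

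**What the plan says.** The Statistical analysis section gives the method for the laboratory outcomes in one sentence: "a repeated measures analysis of variance will be applied". It adds normality tests, states that "Tukey-adjusted p values will be applied to examine differences between treatments", and names the package: "STATGRAPHICS CenturionXVIII software will be used". It gives no model terms, covariance structure, analysis set, missing-sample rule, sensitivity analysis or comparison of dropout by arm. It names no procedure within the package.

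Dropout is foreseen in two places. Under Type of study, "it was determined to take 54 subjects in total with an oversample of 20% (66 individuals in total) to compensate for possible dropouts". Under Target population, "each group with 21 subjects to compensate for possible dropouts and guarantee 18 per group". Type of study also makes blood collection depend on the course of the pandemic. Both sections stratify participants by sex, but sex does not appear in the analysis.

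The number and timing of blood samples are not in the readable text, and the design figure could not be read. Objective 1 and the section on possible results speak of before and after, or of comparison with initial values.

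**The concern.** The only stated response to dropout is to recruit more people. That restores numbers, but it does not restore comparability if the people who leave one yogurt differ from those who leave another. The arms receive different foods, since both oil yogurts have all their milk fat replaced, so unequal dropout is plausible. The documents give no rate by arm.

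A classical repeated-measures ANOVA needs a complete set of samples from each participant, and its arm-by-time term compares raw change from baseline. Two costs follow. If leaving is related to baseline or to an interim value, the contrast among completers is biased. Even if leaving is unrelated to outcome, raw change is less precise than a baseline-adjusted comparison. Because the plan is silent, two analysts could follow it faithfully and analyse different people.

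**Working it through.** **1. The plan's dropout allowance.** 54 × 1.20 = 64.8, which becomes 66 when rounded up to three arms of 22. So 66 is reproduced as a 20% oversample. The loss it tolerates is (66 − 54)/66 = 12/66 = 18.2%. The per-group version tolerates (21 − 18)/21 = 3/21 = 14.3%. An actual 20% loss from 66 would leave 66 × 0.80 = 52.8, below 54.

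The group sizes do not agree with each other: 3 × 21 = 63, and "each treatment group will have 33 people in which the sexes will be equally distributed" would give 3 × 33 = 99. The calculations below use 22 per arm, which is 66/3.

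**2. Assumptions, none of them in the documents.** SD 30 mg/dl at each sample; equal within-person correlation ρ of 0.6 to 0.8; no true effect; 18% dropout in one arm only, so 18 of 22 complete; logistic dropout with slope 0.7 or 1.4 per SD of the driving variable, higher values being more likely to leave.

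**3. Bias of the completer change contrast.**

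| Dropout depends on | Bias of completer change | Samples needed for this to arise |
|---|---|---|
| Baseline level | about 0.7 to 2.3 mg/dl, against benefit | before and after |
| Mid-study change | about 1.1 to 2.7 mg/dl, toward benefit | a mid-study sample |
| Mid-study level | about 0 | a mid-study sample |

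The first row follows from regression to the mean: bias = (1 − ρ) × the amount by which completers' mean baseline falls below that of the whole arm. A bias of 2.3 at ρ = 0.6 corresponds to a shift of 2.3/0.4, about 5.8 mg/dl. A bias of 0.7 at ρ = 0.8 corresponds to 0.7/0.2 = 3.5 mg/dl. Conditioning on baseline removes this bias. In the second row, conditioning on baseline alone is not enough; the model must also use the mid-study sample of those who leave. A likelihood analysis using all samples was essentially unbiased in every scenario.

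**4. Precision, with dropout unrelated to outcome.** For 18 against 22 participants, √(1/18 + 1/22) = 0.318.

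- Raw change: SE = 30 × √(2(1 − ρ)) × 0.318, which is 8.5 at ρ = 0.6 and 6.0 at ρ = 0.8.
- Baseline-adjusted: SE = 30 × √(1 − ρ²) × 0.318, which is 7.6 and 5.7.
- Ratio: √((1 + ρ)/2) = 0.894 and 0.949.

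Estimating the baseline slope uses up a little of this gain, and simulation gives a reduction of about 4% to 10%. Keeping incomplete participants in the model adds only about 1%.

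**5. Size of the bias against noise.** The mid-study-change bias is between 1.1/6.0 = 0.18 and 2.7/8.5 = 0.32 of the standard error of the contrast.

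**The case against.** The strongest reply is that the plan never says incomplete participants are removed. That is correct. A repeated-measures ANOVA fitted as a linear model with subject as a random factor can keep them, and no procedure in the named software is specified. A reader might infer a planned completer analysis from the over-recruitment. That does not follow, because allowing for dropout is routine under any analysis, including intention to treat.

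A reader might also take the 20% as an expected dropout rate of a fifth. It is an oversample against possible loss, equivalent to 14% to 18%, and the Development section describes support for adherence in every phase.

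The mid-study scenario is also open to challenge. The readable text points to before and after samples. Results are shared with participants only in Phase III, so nothing suggests that people would leave because of an interim cholesterol value. This stands: that row of the table is conditional on a sample that may not exist. With two samples, someone who leaves has only a baseline, and little follow-up is lost.

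Finally, the biases are modest and their sign depends on the mechanism. This also stands. The reply does not remove the baseline-related bias, which needs only two samples, or the loss of precision from unadjusted change. Nor does it supply an analysis set.

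**Conclusion.** The point holds as a weakness in the chosen method together with a gap in the specification. The plan foresees loss of about 14% to 18% and names an analysis whose usual form drops incomplete participants and ignores baseline and sex. A better method is available from the same data.

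The size is moderate. Under the stated assumptions the bias is about 0.7 to 2.3 mg/dl from baseline-related dropout. It is about 1.1 to 2.7 mg/dl in the other direction from dropout on mid-study change, if a mid-study sample exists, and about 0 from dropout on mid-study level. The precision gain of about 4% to 10% belongs to baseline adjustment. It should not be read as the benefit of retaining incomplete participants, which is about 1%.

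The documents do not support saying that the plan excludes incomplete participants, or that bias will occur. They support saying that the plan permits both and guards against neither. If dropout depends on values that are never observed, no model in this class corrects it.

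**What to change.** In the Statistical analysis section:

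1. Make the primary analysis a likelihood-based linear mixed model (REML) of all randomised participants in their assigned arm, with arm-by-visit and sex.
2. State how baseline is handled. As a covariate, participants with at least one post-baseline sample contribute. As part of the outcome vector with a common baseline mean, everyone with a baseline sample contributes. With only before and after samples, the model reduces to ANCOVA on baseline and sex.
3. Keep the Tukey adjustment for the arm contrasts.
4. State the missing-at-random assumption.
5. Show the completer repeated-measures ANOVA as a sensitivity analysis.
6. Report dropout by arm, with reasons.

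State the number and timing of blood samples in the text, and reconcile the group sizes (66 in total, 33 per group, 21 per group) so that the dropout allowance is fixed.

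The cost is revised wording, slightly more analysis work and possibly a different package if the named one cannot fit the model. No extra participants, samples or data are needed.

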In this context of promoting healthy eating and based on the characterization of the western diet, which does not meet the daily requirements for essential fatty acids (EFAs) and fat soluble vitamins such as vitamin E, the present research project aims to describe the effect of daily consumption of two fermented dairy beverages supplemented with dietary sources high in tocotrienols and ALA on classical biological markers of cardiovascular disease (CVD) and vitamin E, over a period of three months, in individuals with cardiovascular risk. The products are currently being developed as part of a doctoral thesis in the Food Science and Technology program at the Universidad Nacional de Colombia, Bogotá campus, Faculty of Agricultural Sciences. If satisfactory results are obtained, new dairy products could be developed for the Colombian market, promoting the cultivation of Sacha INchi and Palm by diversifying the use of their fruits as sources of bioactive compounds. The present research proposal aims to answer the following question: what is the effect of consuming yogurts fortified with dietary sources of omega-3 and vitamin E on cardiovascular disease biomarkers and vitamin E in healthy adults?

OBJECTIVES

General: Evaluate the effect of consumption of two fermented dairy beverages fortified with SIO and HPO, on the lipid profile and vitamin E, in individuals at risk of CVD.

Specifics:

1. Describe the health, nutritional status and intake of the individuals before and after the intervention.
2. Establish the changes over time in the lipid profile, Apo A, Apo B and vitamin E in the blood after the intervention.

MATERIALS AND METHODS

The study will be presented to the research and ethics committee of the Faculty of Sciences of the Pontificia Universidad Javeriana. The effect of consumption of fermented dairy beverages fortified with SIO and HPO will be evaluated on the response variables: plasma lipid profile (HDL-C, LDL-C, Triglycerides, TC), Apolipoprotein A, Apolipoprotein B and vitamin E level in blood.

Type of study

An experimental study will be carried out consisting of a controlled clinical trial with three arms, each of which will be determined by the administration of two oils and a control. The oils will be transported into a fermented milk drink. Participants will be selected using a criterion of convenience through a call at the

 
Pontificia Universidad JAVERIANA Colombia
	
Research registration PUJ
	
Version: 1

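### The blood-marker analysis names no treatment contrast and adjusts for neither baseline nor sex; stating a baseline- and sex-adjusted end-of-intervention comparison is a free improvement

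*Combined protocol and SAP*

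**What the plan says.** The inferential plan for the blood markers is two sentences in the Statistical analysis section: "To analyze data from blood samples, a repeated measures analysis of variance will be applied", and "Tukey-adjusted p values will be applied to examine differences between treatments". Normality tests and the software are also named. Model terms, time point and covariates are not.

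Other sections bear on the contrast:

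- The general objective is to "Evaluate the effect of consumption of two fermented dairy beverages fortified with SIO and HPO, on the lipid profile and vitamin E", in a three-arm controlled trial. That calls for a comparison between arms.
- Specific objective 2 is to "Establish the changes over time in the lipid profile, Apo A, Apo B and vitamin E in the blood after the intervention", which points to change.
- Possible research results expects improvement "of the participants compared to the initial values, which would minimize the risk of associated CVD". That is a within-arm comparison, and it shows that baseline values will exist.
- Type of study states: "Individuals will be stratified by sex and will be randomized in equal numbers to each of the three treatment groups". Target population repeats the stratification ("Individuals will be stratified by sex and randomized using the method called") but names the method as unrestricted randomisation.

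No other readable section links these statements to a specific test.

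**The concern.** A repeated-measures ANOVA offers several comparisons that could be called a difference between treatments, and three fit the text:

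1. **Treatment-by-time.** Arms are compared on change from baseline. Baseline is used, but only by subtraction.
2. **Final value.** Arms are compared at the last sample, and baseline is not used.
3. **Treatment main effect.** Arms are compared on the average over all samples, including the one taken before treatment.

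Two analysts following the plan could therefore run different tests on the same data, and the choice could be made after the results are seen. None of the three uses baseline as a covariate, which is normally the more precise use of it, and none includes the stratification factor. The study is also meant to inform later work ("this study will provide a parameter to determine the sample size in subsequent studies"), so readers will need to know which quantity was estimated.

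**Working it through.** **The plan's own figure.** Target population gives 54 subjects, 18 per group, with a 20% oversample to 66. This reproduces: 18 × 1.2 = 21.6, rounded up to 22, and 3 × 22 = 66. The base of 54 cannot be reproduced, because no effect, SD, alpha or power is stated. The check uses 18 per arm, the number the plan aims to retain. (The 21 and 33 per group also stated do not fit 66: 3 × 21 = 63 and 3 × 33 = 99. That is a separate matter.)

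**Assumed inputs.** Two-sided Tukey 5% over three arms; one baseline and one follow-up sample with equal SDs; pre-post correlation r = 0.5, 0.7, 0.8; true difference d = 0.5, 0.8, 1.0 SD.

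**Per-subject variance, in SD², for an estimate of the full effect d**

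- Treatment main effect: the average of two samples has variance (1+r)/2 but carries only d/2. On the full-effect scale the variance is 2(1+r).
- Final value: 1.
- Change (treatment-by-time): 2(1−r).
- Baseline-adjusted ANCOVA: 1−r².

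ANCOVA relative to change is (1−r²)/[2(1−r)] = (1+r)/2 = 0.75, 0.85, 0.90, so its variance is 25%, 15% and 10% lower.

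**Power.** The noncentrality is d/√(2v/18), where v is the variance above. The Tukey critical value is 2.414 on 51 df, or 2.415 on 50 df for ANCOVA. Example at r = 0.7, d = 0.8: change 0.8/√(2×0.6/18) = 3.10, power 75.1%; ANCOVA 0.8/√(2×0.51/18) = 3.36, power 82.4%; main effect 0.8/√(2×3.4/18) = 1.30, power 14.2%.

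Power (%) at d = 0.5 / 0.8 / 1.0 for a marker not selected at entry:

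| r | Change | ANCOVA | Gain (points) | Final value | Main effect |
|---|---|---|---|---|---|
| 0.5 | 19.0 / 49.9 / 72.0 | 25.7 / 64.0 / 84.9 | 6.7 / 14.1 / 12.9 | 19.0 / 49.9 / 72.0 | 6.8 / 16.1 / 25.7 |
| 0.7 | 32.5 / 75.1 / 92.4 | 38.4 / 82.4 / 96.0 | 5.9 / 7.3 / 3.6 | 19.0 / 49.9 / 72.0 | 6.2 / 14.2 / 22.5 |
| 0.8 | 48.8 / 91.2 / 98.9 | 53.8 / 94.0 / 99.4 | 4.9 / 2.7 / 0.6 | 19.0 / 49.9 / 72.0 | 5.9 / 13.4 / 21.2 |

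The difference detectable with 80% power at r = 0.5 / 0.7 / 0.8 is 1.09 / 0.84 / 0.69 SD for change and 0.94 / 0.78 / 0.65 SD for ANCOVA.

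**Corrections to the gain**

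- *Chance baseline imbalance.* The formula 1−r² leaves out its cost. Simulation at r = 0.5 gives ANCOVA 24.7 / 63.3 / 83.9%, so the gain is smaller by up to about 1 point.
- *Entry threshold on total cholesterol.* If the qualifying value is also the baseline, selection narrows its spread. Simulation with a cut at 200 mg/dl (assumed mean 180-190, SD 35, r 0.7-0.8) gives change 36-53 / 80-93 / 95-99% and ANCOVA 38-53 / 81-94 / 96-99%, a gain of 0-2 points.
- *Sex.* It costs one degree of freedom. If it explains nothing, power changes by 0 to −0.05 points. If it explains 5% of residual variance, power rises by 0.2 to 2.5 points.

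**Main-effect reading.** With one follow-up sample the expected estimate is d/2, and power at 0.8 SD is 13-16%. With two follow-up samples it keeps 2/3 of d, and power at 0.8 SD is 25-33%.

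**The case against.** The strongest reply is that the plan already implies its contrast. Objective 2 speaks of changes over time, the expected results refer to initial values, and treatment-by-time is the usual test of interest in a repeated-measures ANOVA. On that reading baseline is already used, and the gain from ANCOVA is modest and close to nil for total cholesterol in one plausible case. More retained participants would shrink it further in places: at 33 per arm and r = 0.7 it is 8.2 / 2.0 / 0.2 points. The case for including sex is also less than firm, because stratification is paired with unrestricted randomisation and Phase II repeats the latter without mentioning strata.

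Most of this stands, and it sets the size of the point. It does not remove the gap: the contrast is still unstated, and objective 2 does not say what is compared between arms.

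Stronger readings are tempting but not supported:

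- *The trial will run at 13-16% power.* This needs the main-effect test, which no section states and which objective 2 makes less likely.
- *The randomised comparison is biased.* Change and final value are unbiased for the treatment effect. Only the main effect is attenuated.
- *Later trials will be missized by a known factor.* The sample-size text promises only a parameter and does not say which.
- *Falls in cholesterol within arms will be an artefact of selection.* The readable text does not say whether the qualifying value serves as baseline.
- *Sampling times are missing.* They may be in the study-design figure, which could not be read.

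**Conclusion.** The point holds as a free improvement. That the contrast and covariates are unstated is certain from the text; how much adjustment gains is not, because every numerical input is assumed.

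Against the likeliest reading, ANCOVA lowers variance by 10-25% and adds about 1-14 points of power for an unselected marker, less up to about 1 point for chance imbalance. For total cholesterol it adds 0-2 points if the qualifying value is the baseline. ANCOVA is not expected to lose precision materially in any of these settings. Sex adds between about 0 and 2.5 points; the reason to include it is consistency with the stratified randomisation more than power.

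The larger loss is conditional. If the Tukey tests were run on the treatment main effect, the pre-treatment sample would be averaged in. With one follow-up sample the reported difference would be half the treatment effect, which is attenuation and not only lost precision. The wording permits this, and that is reason enough to exclude it in writing.

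**What to change.** Replace the two analysis sentences with wording such as:

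> For each blood marker, the end-of-intervention value will be analysed by ANCOVA with treatment arm as factor and baseline value and sex as covariates (with more than one post-baseline sample, a mixed model with treatment-by-time and the same covariates, with the contrast at the last sample). Tukey-adjusted p values will be applied to the adjusted differences between arms, including SIO versus HPO. Conclusions about benefit will rest on the adjusted difference versus control; within-arm change will be descriptive.

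Tukey is kept because the plan compares all treatments, including the two oils with each other.

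This wording fixes a unique time point only once the duration is settled. The paragraph before Objectives gives three months, while Phase II supplies the drinks for one month. The two passages must be reconciled.

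Cost: analysis wording only, best settled before any outcome data are seen. Sex is recorded at screening and initial marker values are already planned, so no participants, visits or samples are added. The last sentence of the proposed text also sets which comparison supports a claim of benefit, and the investigators should adopt it knowingly.
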